9.7.2 Missing data

In general, imputation of missing data will not be applied. In addition to that, no “Last observation carried forward” (LOCF) approach will be applied.

Implausible values will be set to missing values, as no correcting of values is possible due to the nature of the dataset. The defined lower and upper bounds for an acceptable range of continuous study variables are listed in Table 1; note that these ranges are defined with regards to obvious documentation mistakes.

Table 1: Lower and upper bounds for continuous study variables

Variable	Unit	Acceptable range
Age	Years	40 to 110
Prescriptions of CV or AD drugs per patient year	Number	1 to 300

In case of missing data for specific variables, reporting category “not reported/not available” will be used.

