Research question and objectives:	
Description of the real-life treatment of adult patients with T2DM receiving empagliflozin, comparing the characteristics of patients starting empagliflozin in three time intervals:
 
 - The first analysis will include the patients receiving Empagliflozin before the EMPA-REG-OUTCOME study was published (time until mid-Sept. 2015; "Cohort 1"). - The second analysis will include patients receiving Empagliflozin starting from the EMPA-REG-OUTCOME study being published until CV Label Change (time from mid-Sept. 2015-mid-Jan. 2017; "Cohort 2"). - The third analysis will include all patients receiving Empagliflozin starting from mid-Jan. 2017 until last available data cut ("Cohort 3").
Study design:	
Retrospective non-interventional cross-sectional study using real-world data from German patient registries. Data will be provided by the largest German T2D patient registries DPV& DIVE covering more than 500,000 patients.

Population:	
Inclusion criteria:
 
 • Adult patients with at least two outpatient T2DM diagnoses (ICD E11.-) in two different quarters and/or at least one inpatient T2DM diagnosis (ICD E11.-) – AND – • At least one prescription of an empagliflozin-containing antidiabetic drug: Jardiance® (Empagliflozin, ATC A10BK03, former

	A10BX12) or Synjardy® (Empagliflozin/Metformin, ATC A10BD20)
--	---

Exclusion criteria

- Any diagnosis of T1DM.

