9.2 SETTING AND INCLUSION/EXCLUSION CRITERIA

Description of the real-life treatment of adult patients with T2DM receiving empagliflozin, comparing the characteristics of patients starting empagliflozin in three time intervals:

- The first analysis will include the patients receiving Empagliflozin before the EMPA-REG-OUTCOME study was published (time until mid-Sept. 2015; “Cohort 1”).
- The second analysis will include patients receiving Empagliflozin starting from the EMPA-REG-OUTCOME study being published until CV Label Change (time from mid-Sept. 2015-mid-Jan. 2017; “Cohort 2”).
- The third analysis will include all patients receiving Empagliflozin starting from mid-Jan. 2017 until last available data cut (“Cohort 3”).

Inclusion criteria:

- At least two outpatient T2DM diagnoses (ICD E11.-) in two different quarters and/or at least one inpatient T2DM diagnosis (ICD E11.-)
- At least one prescription of an empagliflozin-containing antidiabetic drug: Jardiance® (Empagliflozin, ATC A10BK03, former A10BX12) or Synjardy® (Empagliflozin/ Metformin, ATC A10BD20)

Exclusion criteria

- Any diagnosis of T1DM

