9.3.1.2 Secondary outcomes

- Age (<65; 65 – <75; 75 – 80 , >80)
- Gender
- Weight [kg]
- Height [cm]
- HbA1c [% or mmol/ mol], FPG (available in subgroup only)
- Duration of diabetes (time since diagnosis)
- Previous glucose-lowering treatment
- Dosage of empagliflozin (10mg vs 25mg) (available in subgroup only)
- Participation in Disease Management Programme (DMP) Type 2 Diabetes (from DPV registry)
- Hospitalizations (from DPV registry)

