9.10 SUBJECTS

All patients with T2DM from the DPV & DIVE registries receiving Empagliflozin will be included. The patients will be divided in three cohorts based on the time point of Empagliflozin treatment start to better identify the differences between these cohorts.

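### Table 1 blanks every age below 40 as a recording error, although the study covers all adults with type 2 diabetes on empagliflozin

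*Combined protocol and SAP*

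**What the plan says.** Section 9.7.2 (Missing data) gives the cleaning rule: "Implausible values will be set to missing values, as no correcting of values is possible due to the nature of the dataset". Table 1 lists the acceptable range for age as 40 to 110 years, and the accompanying text explains the purpose of the limits: "note that these ranges are defined with regards to obvious documentation mistakes". The section rules out imputation in general. It closes with a per-variable provision, beginning "In case of missing data for specific variables", under which such values are reported in a separate not-reported category. Section 9.7.1 adds that the analysis is complete case.

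The population is described elsewhere without a numeric age limit:

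- Section 4 (Abstract), inclusion criteria: "Adult patients with at least two outpatient T2DM diagnoses" and/or one inpatient diagnosis, plus at least one prescription of an empagliflozin-containing product.
- Section 9.2, lead sentence: "Description of the real-life treatment of adult patients with T2DM receiving empagliflozin". The listed criteria there contain no age item, and the only exclusion is "Any diagnosis of T1DM".
- Section 9.10: "All patients with T2DM from the DPV & DIVE registries receiving Empagliflozin will be included".
- Section 9.3.1.2 lists age as a secondary outcome in bands, "Age (<65; 65 – <75; 75 – 80 , >80", the lowest of which is open downwards.
- Annex 2 (ENCePP checklist), item 4.2.2, answers that the population is defined by age in section 9.2.

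**The concern.** A plausibility bound is meant to lie outside the range of values an eligible patient can have. The upper bound of 110 does. The lower bound of 40 does not: it cuts into the adult range that the protocol itself sets as its population. A correctly recorded age of 35 in an eligible patient would be treated as a documentation error and removed.

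The loss is one-sided. Only values at the young end go, so the reported age distribution can only move upward and the under-65 share can only fall. That movement comes from the cleaning rule and not from the patients or from errors in the data. The study's purpose is to describe who receives empagliflozin, and age is one of its listed descriptors.

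**Working it through.** **Text check.** The bound of 40 was compared with every place where the protocol defines or describes the population.

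| Place | Age limit stated |
|---|---|
| 4, inclusion criteria | adult, no number |
| 9.2, lead sentence | adult, no number |
| 9.2, listed criteria | none |
| 9.2, exclusion | none (type 1 diabetes only) |
| 9.3.1.2, lowest age band | under 65, open downwards |
| 9.10 | none |
| Annex 2, item 4.2.2 | refers to 9.2, which gives no number |
| 9.7.2, Table 1 | 40 to 110 |

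The floor of 40 appears only in Table 1, where it is presented as error cleaning and not as eligibility. An eligible adult under 40 is therefore included under sections 4, 9.2 and 9.10, but the age value is deleted under section 9.7.2.

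**Size (illustration only).** The protocol has no figure of its own to reproduce here. The one input it supplies is the study size, about 7,900 (section 9.5). The rest is assumed: ages normal, SD 10 or 12 years, and a true share *s* under 65 of 40%, 50% or 60%.

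Formulas:

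- mean = 65 − SD × z(*s*), where z is the standard normal quantile
- share under 40: *p* = Φ((40 − mean)/SD)
- ages lost = 7,900 × *p*
- fall in the under-65 share among known ages = *s* − (*s* − *p*)/(1 − *p*) = *p*(1 − *s*)/(1 − *p*)
- fall if the not-reported category stays in the denominator = *p*
- rise in the median = SD × z(0.5 + *p*/2)

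| SD | *s* | Mean | *p* | Ages lost | Fall, known ages (points) | Rise in median (years) |
|---|---|---|---|---|---|---|
| 10 | 40% | 67.5 | 0.295% | 23 | 0.18 | 0.04 |
| 10 | 50% | 65.0 | 0.621% | 49 | 0.31 | 0.08 |
| 10 | 60% | 62.5 | 1.233% | 97 | 0.50 | 0.16 |
| 12 | 40% | 68.0 | 0.973% | 77 | 0.59 | 0.15 |
| 12 | 50% | 65.0 | 1.861% | 147 | 0.95 | 0.28 |
| 12 | 60% | 62.0 | 3.363% | 266 | 1.39 | 0.51 |

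Worked example, last row: mean = 65 − 12 × 0.2533 = 61.96; (40 − 61.96)/12 = −1.830; Φ = 0.03363; 7,900 × 0.03363 = 266. The fall among known ages is 0.03363 × 0.40/0.96637 = 0.0139, so the share goes from 60.0% to 58.6%. With not-reported patients kept in the denominator it goes from 60.0% to 56.6%. About 1 of the 266 would be under 18, so nearly all the deleted values belong to adults.

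Without any distributional assumption, assumed shares under 40 of 1%, 3% and 5% give 7,900 × 0.01 = 79, 7,900 × 0.03 = 237 and 7,900 × 0.05 = 395 ages lost.

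**The case against.** **Eligibility and value cleaning are separate steps.** A 35-year-old stays in the study and only the age is blanked, so both rules can be carried out. That is correct, and the problem is best described as an unjustified bound that is inconsistent with the stated population. It remains a problem, because the only reason given for the bound does not apply to a valid age in an eligible patient.

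**40 may be an intended minimum age.** If so, it belongs among the inclusion criteria. Blanking the value does not exclude the patient, so Table 1 would not achieve that aim either.

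**The size is assumed.** This stands. The SD, normality and under-65 share have no source in the protocol, and the count varies more than tenfold across the assumed range. The figures show the direction and a rough order of magnitude. Section 9.3.1.2 lists age only in bands, so the median shift matters only if a median is reported.

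**The effect on the primary outcomes is not settled by the text.** The per-variable wording in section 9.7.2 suggests that a blanked age leaves the comorbidity and co-medication percentages untouched. Section 9.7.1, however, calls for complete case analysis without saying whether this applies per variable or across all variables. Under the second reading, patients under 40 would drop out of the primary outcomes as well. This makes the harm potentially larger, not smaller; the assessment here uses the milder reading.

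**Conclusion.** The concern holds and is minor. Table 1 treats valid ages of eligible adults under 40 as recording errors, and no section of the protocol supports that floor. The inconsistency is certain from the text alone. Its size is not known: under the stated assumptions it is 23 to 266 lost ages of 7,900, a fall in the under-65 share of about 0.2 to 1.4 points among known ages (0.3 to 3.4 points with the not-reported category in the denominator), and a rise in the median of about 0.04 to 0.5 years. A skewed age distribution would give other figures. On the per-variable reading of section 9.7.2 the effect is confined to age as a secondary outcome. No bias in the comparison between the three cohorts is claimed.

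**What to change.** Reconcile Table 1 with the eligibility criteria in one of two ways:

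1. Change the lower age bound in Table 1 to the adult limit. The protocol gives no number for this; 18 is the usual reading and should be written out.
2. If a minimum age of 40 is intended, state and justify it as an inclusion criterion in sections 4 and 9.2, and stop describing younger ages as documentation mistakes.

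In either case, put the age criterion among the listed criteria of section 9.2, so that checklist item 4.2.2 is accurate, and state in section 9.7.1 whether complete case applies per variable. The cost of the main change is one table cell or one added criterion, with no new data; the two clarifications take a sentence each.

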9.3.1.1 Primary outcomes

- Previous occurrence (percentages) of
 - Typical CV comorbidities:
 - MI
 - Stroke
 - CAD
 - PAD
 - CHF (form (HFrEF/ HFpEF)

Proprietary confidential information © 2020 Boehringer Ingelheim International GmbH or one or more of its affiliated companies

- Other typical diabetes complications:
 - Neuropathy
 - Nephropathy / Renal function (eGFR, micro-/ macroalbuminuria)
 - Diabetic foot syndrome
 - Retinopathy (background and proliferative)
- Antidiabetic and cardiovascular co-medication (lipid-lowering agents, RAAS blockers, other antihypertensives, beta blockers, diuretics, antiplatelets and anticoagulants)

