9.7 DATA ANALYSIS

9.7.1 Main analysis

Variables will be assessed in half-yearly periods after index date (date of first prescription of empagliflozin), for total study population and separated by study cohort.

Anonymized data from the DIVE and the DPV registries will be combined; nonparametric descriptive analyses will be used. Group comparison will be based on Wilcoxon rank sum test (continuous variables) and X²-test for binary/categorial values. Analysis will be implemented using SAS 9.4. Complete case analysis will be used.

Analysis will be done by an experienced biostatistician with detailed knowledge of the DIVE and the DPV registries. A second independent programmer will check the generated SAS code for inconsistencies. The medical team (

will evaluate the results from a clinical background to ensure plausibility.

Quality assurance and control will be the responsibility of the medical team (

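### Table 1's lower bound of 1 for prescriptions per patient-year sets genuine zero and fractional rates to missing, and could reach the co-medication percentages under conditions the plan leaves open

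*Combined protocol and SAP*

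**What the plan says.** Section 9.7.2 introduces Table 1 with the words "The defined lower and upper bounds for an acceptable range of continuous study variables are listed in Table 1". One of its two rows is "Prescriptions of CV or AD drugs per patient year", with an acceptable range of 1 to 300. The consequence of falling outside is stated plainly: "Implausible values will be set to missing values, as no correcting of values is possible due to the nature of the dataset". The purpose is stated too: "note that these ranges are defined with regards to obvious documentation mistakes".

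Three other statements decide what happens next. Section 9.7.1 says "Complete case analysis will be used". Section 9.7.2 says "In general, imputation of missing data will not be applied". Section 9.7.2 also says "In case of missing data for specific variables, reporting category “not reported/not available” will be used".

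Section 9.3.1.1 makes co-medication a primary outcome, listed by drug class: "Antidiabetic and cardiovascular co-medication (lipid-lowering agents, RAAS blockers, other antihypertensives, beta blockers, diuretics, antiplatelets and anticoagulants". The prescription rate itself is not in the variable list of the abstract (section 4), nor in sections 9.3.1.1 or 9.3.1.2.

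**The concern.** A range check should remove values that cannot be true. An upper limit of 300 can be read that way; a lower limit of 1 cannot. A patient without any CV drug has a true CV rate of 0, and a patient with few recorded prescriptions over a long observation time has a true rate below 1. The rule treats both as documentation mistakes and deletes them.

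The first consequence concerns the rate itself. Only low values are lost at this end, so what remains is shifted upwards.

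The second consequence is conditional. If the rate also decides who counts as a co-medication user, the patients set to missing are mainly non-users or sparse users. Under complete case analysis they would leave the denominator of a primary outcome. The shift could also differ between the three cohorts if observation time or non-use differs between them.

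**Working it through.** **Inputs from the plan.** Range 1 to 300, out-of-range values set to missing, no imputation (9.7.2). Complete case analysis and half-yearly periods after the index date (9.7.1). A separate reporting category for missing data (9.7.2). At least one empagliflozin prescription required for entry (9.2). About 7,900 patients (9.5).

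**Not in the plan.** The share of patients using each drug, the share with a rate below 1, the person-time used for the rate, and whether CV and antidiabetic drugs are counted together, separately or by class. Annex 2 (checklist section 5) adds that there is no follow-up period, so the person-time is open. The plan gives no prescription rate or co-medication percentage, so there is no figure of its own to reproduce.

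**Step 1: which genuine values fall out.** Rate = k/T, for k prescriptions in T years.

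| k | T (years) | k/T | Result |
|---|---|---|---|
| 0 | any | 0 | missing |
| 1 | 0.5 | 2.00 | kept |
| 1 | 1 | 1.00 | kept |
| 1 | 1.5 | 0.67 | missing |
| 2 | 2 | 1.00 | kept |
| 2 | 4 | 0.50 | missing |
| 3 | 4 | 0.75 | missing |

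In a half-year window the smallest non-zero rate is 1/0.5 = 2, so there the bound removes zeros and nothing else. In longer windows it also removes sparse records. Two prescriptions are kept over two years and lost over four, so the effect depends on observation length. If person-time runs to a common data cut, the earlier cohorts are observed for longer and are hit more often.

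**Step 2: effect on the rate.** If the lowest share z is deleted, the median of what remains is the percentile z + (1 − z)/2 of the full distribution. For assumed z = 10%, 20% and 30% that is the 55th, 60th and 65th percentile instead of the 50th. If the deleted values are all zeros, the mean is multiplied by 1/(1 − z): 1.11, 1.25 and 1.43.

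**Step 3: effect on co-medication percentages, if the rate feeds them.**

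- *Bound applied to all CV drugs together, complete case.* Reported share = p/(1 − z), where p is the true share using a given drug and z the share with no CV drug. With assumed p = 50%: 0.50/0.90 = 55.6%, 0.50/0.80 = 62.5%, 0.50/0.70 = 71.4%.
- *Bound applied to each class, complete case.* Reported share = p/(p + (1 − p)(1 − f)), where f is the share of non-users deleted. With p = 50%: 57.1% at f = 25%, 66.7% at f = 50%. At f = 100% it is 100% whatever p is.
- *CV and antidiabetic drugs counted together, index prescription included, complete case.* Inflation = m(p_rest − p_low), where m is the share with a rate below 1. With assumed p_rest = 70%: 0.02 × (0.70 − 0.30) = 0.8 points, up to 0.10 × (0.70 − 0) = 7.0 points.
- *Missing category kept in the denominator.* The user percentage stays at p. Genuine non-users are then shown as unreported: up to 3,950 of 7,900 if p = 50% and all non-users are affected.

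**Step 4: do the documents supply the links?** Section 9.3.1.1 gives co-medication as drug classes and 9.7.1 plans a chi-square test for categorical values, while Table 1 is limited to continuous variables. No section says the one is derived from the other. The row label joins CV and antidiabetic drugs and does not say that they are counted apart. On the denominator, 9.7.1 and the last sentence of 9.7.2 point in different directions.

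**The case against.** A reader might infer that the rule makes non-users drop out and therefore inflates the primary co-medication percentages. The case against that inference is strong, and most of it stands.

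- Co-medication can be read directly from drug-class entries without any rate, and the plan nowhere says otherwise.
- The row label covers both drug groups, and every included patient has at least one empagliflozin prescription. On a combined count that includes it, nobody is a complete non-user, and a patient with no CV drug but regular antidiabetic prescriptions stays in range.
- The separate reporting category may keep patients in the denominator, in which case the user percentage is not inflated.
- The class-by-class reading in full gives 100% for every class, a result so implausible that it is unlikely to be what was meant.

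None of this rescues the bound. The argument that the count is never zero holds only over a window that contains the index prescription; a later half-year without a recorded prescription is still deleted. If the rate feeds nothing, the row has no purpose. If missing values stay in the denominator, genuine non-users are mislabelled as unreported.

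The objection also limits the remedy. Declaring every unrecorded prescription to be non-use would carry its own risk. Section 9.3.1.2 shows that recording is uneven: some variables exist only in a subgroup or only in DPV. Where the medication record is incomplete, that rule would bias co-medication downwards.

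**Conclusion.** The lower bound of 1 is wrong for its stated purpose: 0 and rates below 1 can be genuine. Where they occur, any summary of the rate is biased upwards. This conclusion needs no assumption beyond the occurrence of such values.

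Inflated co-medication percentages are possible but not established. They require that co-medication is derived from the range-checked rate, that the bound is applied to CV drugs separately or by class, and that missing values leave the denominator. A combined count would need the first and third, and would mainly affect sparse records. The documents are silent on the first two conditions and inconsistent on the third.

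The size cannot be derived from the documents. The range 55.6% to 71.4% for a true 50%, and the 0.8 to 7.0 points on the combined count, show what the mechanism could do with assumed inputs; they are not estimates for this study.

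**What to change.** In section 9.7.2, Table 1, change the lower bound of the prescription row to 0. If the rate is not analysed, delete the row. If it is kept, define the count (CV and antidiabetic together, separately or by class) and its person-time.

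State that the range check does not apply to co-medication status, which is derived as yes/no by drug class at index. Count a patient as a non-user only where the registry's medication record is available; otherwise use the existing category for missing data.

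Reconcile the complete case rule in 9.7.1 with that category in 9.7.2 by naming the denominator of each reported percentage.

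The cost is one table cell and a few sentences, with no further data to collect. The one practical task is to define, for each registry, when a medication record counts as available. That step is needed so that missing documentation is not counted as non-use.

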9.8 QUALITY CONTROL

Analysis will be done by an experienced biostatistician with detailed knowledge of the DIVE and the DPV registries. A second independent programmer will check the generated SAS code for inconsistencies. The medical team (will evaluate the results from a clinical background to ensure plausibility/validity.

Study design and study conduct will be in line with legal and regulatory requirements, as well as with scientific purpose, value and rigor and follow generally accepted research practices such as Good Pharmacoepidemiology Practices (GPP) issued by the International Society for Pharmacoepidemiology (ISPE), the International Society for Pharmacoeconomics and Outcomes Research (ISPOR) guidelines, Pharmaceutical Research and Manufacturers Association (PhRMA) guidelines and similar rules.

9.9 LIMITATIONS OF THE RESEARCH METHODS

DPV & DIVE data are observational data; treatment, especially the use of Empagliflozin, is not randomized to the patients. This has to be kept in mind for the interpretation of the results. Also, a systematic difference (bias) between patients documented in the registry versus patients treated at facilities not participating in either of the registries cannot be entirely excluded.

9.10 SUBJECTS

All patients with T2DM from the DPV & DIVE registries receiving Empagliflozin will be included. The patients will be divided in three cohorts based on the time point of Empagliflozin treatment start to better identify the differences between these cohorts.

